### 7.2 Secondary endpoints

#### 7.2.1 24-weeks PFS rate

The definition of 24-week PFS rate is the percentage of patients who had **NOT** has an event before or at 24-week after treatment starts. An event is defined as follows:

- Disease progression (PD according to RECIST 1.1)
- Death due to any cause

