
Therapeutic Assessments
	
 
1. Therapeutic assessment by CT or MRI will be performed from week 8, 16, and 24 and then every 12 weeks afterwards. A +/- 3 days window is allowed.
 
2. Biopsy will be performed at baseline and after the first tumor assessment (optional)
 

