#### 6.3.2 Assessment schedules

- Tumor assessment by CT scan or MRI will be obtained at baseline (as specified in section 6.1), 8 weeks, and 16 weeks and 24 weeks and every 12 weeks afterwards. A +/- 7 days window is acceptable.
- Investigator assessment of the tumor response will be recorded and the investigator will decide treatment plan according to local assessment.

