#### **6.5 Summary Table**

Table 8 Flow sheet of LEADER Trial

Study	Screening		L + E Cycle 1 (21 days/cycle)			L + E Cycle 2 (21 days/cycle)			L+E Cycle 3 and afterwards (21 days/cycle)			End of Treatment i
			1 a	2	3	4	5	6	7	8	9	
Week	0		1 a	2	3	4	5	6	7	8	9	
Time window	-28~0	-14~0	-3~0	-3~0		-3 ~ +3 k	-3 ~ +3 k		-3 ~ +3 k	3 ~ +3 k		
Informed consent	X											
Inclusion/ Exclusion criteria	X											
Medical history b	X											
Physical examination		X	X	X		X	X		X j			X
Performance status (KPS or ECOG)		X	X			X						X
Laboratory assessments												
Hematology (CBC+diff, plts)		X	X	X		X	X		X			X
Serum chemistry c		X	X	X		X	X		X			X
Coagulation		X										
Urinalysis		X				X			X			X
Pregnancy test d		X	X									
Adverse event assessment e		X	X	X	X	X	X	X	X	X	X	X
Tumor assessment f		X								X		
12-Lead ECG g		X				X			X			X
Biopsy h	X (within 4 weeks)									X h		

L: Lenvatinib, E: eribulin, CBC: complete blood chemistry, ECG: electrocardiogram, KPS: Karnofsky performance status, ECOG: Eastern Cooperative Oncology Group

- a Medical history, physical examination, vital signs, Karnofsky or ECOG performance status, ECG, adverse events assessment, and concomitant medications may be omitted on Day 1 if these evaluations have been completed within 14 days prior to starting study treatment. Hemogram and biochemistry needs to be repeated within 3 days of Day 1.
- b History only – survival status, details of recurrent/metastatic disease, new treatments.
- c Serum creatinine and creatinine clearance, BUN, Electrolytes (Na, Ca, K, Mg), Total protein, Albumin, Alkaline phosphatase, AST and ALT, Total bilirubin, and LDH.
- d Women of childbearing potential
- e AEs recorded at every visit, and as needed at any time during the treatment. After end of treatment, AEs will be recorded until 28 days after end of treatment (EOT). The investigator is not required to actively monitor patients for adverse events afterwards. However, the sponsor should be notified if the investigator becomes aware of any post-study serious adverse events or non-serious adverse events of special interest. Other AE reporting details please refer to section 9.3.

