- f Tumor assessment by CT or MRI will be carried out on week 8, week 16, week 24, and every 12 weeks afterwards with a +/- 7 days window. The week 8 and week 24 images will be sponsored by the study and week 16 and images after week 24 will be performed according the National Health Insurance Payment system. If a patient reached CR or PR according to RECIST on the 8-, 16-, or 24-week cycle, a confirmed imaging more than 4 weeks later will be sponsored by the study.
- g 12-Lead ECG will be performed before every cycle to monitor the QTc for the first 4 cycles, then every 9 weeks afterwards.
- h The first biopsy will be performed within 4 weeks of treatment starts, the second biopsy will be taken after 1st tumor assessment. At least 10 patients are required to take the pre-treatment biopsy and the second biopsy after treatment is optional but strongly suggested.
- i Survival follow-up interval is 8 weeks +/- 1 weeks for at least 6 months or death
- j If in later cycles patient is using only lenvatinib as single agent treatment, D8 visit and blood test could be omitted
- k two eribulin injections should be at least  $\geq 5$  days apart

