#### 7.2.3 PFS and OS

PFS is measured from the time of randomization to the time of disease progression (either CNS or extra-CNS, according to RECIST 1.1), or death due to any cause. Patients who have not had an event at the time of data analysis will be censored at the date on which they are

last known to be alive and event-free, on or before the clinical data cutoff date of the respective analysis.

OS is measured from the time of randomization to the time of death. Patients who had not recorded a death event at the time of statistical analysis will be censored at the last time point the patient was known to be alive.

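### The 24-week PFS rate counts patients who leave tumor assessment event-free before week 24 as progression-free, and the plan does not fix when week 24 falls

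*Combined protocol and SAP*

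**What the plan says.** Section 7.2.1 takes the share of all patients, and the only failures are those for whom the record shows PD by RECIST 1.1 or death; the cut-off is that the patient "has an event before or at 24-week after treatment starts". It names no estimator, no rule for a missing week-24 scan and no rule tying a scan to its visit. Section 8.2.1 adds only descriptive statistics with confidence intervals.

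Section 6.3.2 schedules scans at baseline and then "8 weeks, and 16 weeks and 24 weeks and every 12 weeks afterwards", and adds "A +/- 7 days window is acceptable". Footnote f of the Summary Table (6.5) agrees: "every 12 weeks afterwards with a +/- 7 days window". The Synopsis differs: "A +/- 3 days window is allowed".

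Section 7.2.3 has a censoring rule, but for PFS as a time-to-event endpoint: patients without an event are censored when "last known to be alive and event-free, on or before the clinical data cutoff date of the respective analysis". It sets the clock as follows: "PFS is measured from the time of randomization to the time of disease progression". OS starts at the same point. Section 4.1 describes a single-arm study.

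**The concern.** The rule in 7.2.1 treats absence of a recorded event as proof of being progression-free. Section 5.5 lets patients stop therapy for toxicity, withdrawal or physician judgement, so some will stop without PD. Section 6.3 is headed as assessment during treatment, and 6.3.4 mentions only survival follow-up afterwards. A patient who stops event-free at week 10 and progresses unseen at week 18 is then a success at week 24. A leaver who dies by week 24 is classed correctly, as is anyone with PD on an earlier scan.

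The cut-off may also fall inside the window of the scan that decides the endpoint. PD seen a few days after the cut-off on a compliant scan would then be missed.

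There is no control arm to share such a shift, so it passes straight into the reported rate. Two analysts could also class the same patient differently.

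**Working it through.** The documents give no figure for this rate, so there is none to reproduce. The sizes below are illustrations under stated assumptions.

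**Inputs.** Median PFS 4.6 months (Introduction, Background; reported there for pazopanib, so borrowed). Assumed: exponential PFS, a 30.44-day month, all events found by scan, scan dates uniform over the whole days of the window. N = 27 evaluable (8.1).

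Daily hazard: ln 2 / (4.6 × 30.44) = 0.004950. Event-free share over one 56-day interval: q = exp(−0.004950 × 56) = 0.7579. Hence S(56) = 75.79%, S(112) = q² = 57.44%, S(168) = q³ = 43.53%. The last is the true rate.

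**Missing scans alone** (in-window scans assigned to their scheduled day). Let 10% of those still event-free leave after each of weeks 8 and 16.
- Leave at week 8: 0.10 × 75.79 = 7.58% of patients.
- Leave at week 16: 0.10 × 0.90 × 57.44 = 5.17%.
- Stay and are event-free at week 24: 0.81 × 43.53 = 35.26%.
- Plain percentage: 7.58 + 5.17 + 35.26 = 48.01%, which is **+4.5 points**.

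In general the excess is 0.10·q(1 − q²) + 0.09·q²(1 − q). At a 3-month median (q = 0.6537) it is 3.74 + 1.33 = 5.1 points; at 10 months (q = 0.8803) it is 1.98 + 0.84 = 2.8. With 20% leaving each time, at 4.6 months: 0.20·q(1 − q²) + 0.16·q²(1 − q) = 8.7 points.

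Per patient, with N = 27: one leaving event-free at week 8 adds an expected (1 − q²)/27 = 1.6 points, and one leaving at week 16 adds (1 − q)/27 = 0.9. A patient actually misclassified adds 1/27 = 3.7.

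**Does the 7.2.3 rule repair this?** It depends on how the rule is read.
- Censoring at the last survival contact: leavers stay in the risk set past week 24 and can show no PD, so Kaplan-Meier returns 48.01% again (+4.5).
- Censoring at the last tumor assessment: each interval uses only patients actually assessed, so the estimate is q × q × q = 43.53% (0.0).

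**Scan timing alone** (nobody leaves).
- *Elapsed-day reading, ±7 days.* Compliant scans fall on days 161–175, and 7 of 15 are after day 168. For those, the patient counts as progression-free if clear at the week-16 scan (57.45% averaged over its window). For the other 8, the average is 44.29%. Result: 8/15 × 44.29 + 7/15 × 57.45 = 50.43%, or **+6.9**.
- *Elapsed-day reading, ±3 days.* Scans on days 165–171: 4/7 × 43.86 + 3/7 × 57.44 = 49.68%, or **+6.1**.
- *Flow-sheet anchor.* Week 1 is Cycle 1, so week 24 begins 23 × 7 = 161 days after first dose. With the window centred there, scans fall on days 154–168 and none is late. The average is 45.08%, or **+1.5**. This comes from looking early, and assigning scans to visits does not change it.
- *Visit reading.* PD on any in-window week-24 scan is an event, so there is no late-scan error.

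**Both together, 10% leaving.** Elapsed-day, ±7: 7.58 + 5.17 + 0.81 × 50.43 = 53.60%, or +10.1. Flow-sheet anchor, with S(49) = 78.46% and S(105) = 59.47%: 7.85 + 5.35 + 0.81 × 45.08 = 49.71%, or +6.2.

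For scale, the standard error is √(0.4353 × 0.5647 / 27) = 9.5 points.

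**The case against.** A reader might infer that late but compliant scans are definitely miscounted. The documents do not support that. No day number is printed for week 24. Footnote f uses the 24-week label for a visit, and the only calendar, the flow sheet, counts from week 1. Two of the three readings remove the late-scan error. What stands is that 7.2.1 does not choose between them and that the windows conflict.

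A reader might also infer that everyone without a week-24 scan is miscounted. Patients with earlier PD or death are counted correctly; only those with no recorded event are affected.

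That imaging ends with treatment is an inference from the heading of 6.3 and from 6.3.4. Section 6.3.2 sets no end to its 12-weekly scans, so the affected group may be small, and the documents give no count. This limits the size but not the rule: anyone who does leave unassessed is counted as a success.

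One could read the rate as the 7.2.3 PFS endpoint evaluated at 24 weeks, with its censoring. Section 7.2.1 says percentage of patients and does not invoke that rule, and the rule does not say whether its date is a scan or a survival contact.

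Finally, every size rests on a borrowed median and assumed dropout. The 27 patients are those left after the plan's own 10% drop-out allowance. Scan-detected PFS always carries some delay. These points stand, and the base shifts are below one standard error. They are nevertheless systematic and run in one direction.

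**Conclusion.** The concern holds for missing assessments under any meaning of week 24. The plain percentage can only overstate the rate, by about 4.5 points at 10% leaving per visit and a 4.6-month median (2.8 to 5.1 across medians of 10 to 3 months). The scan-timing part is conditional: 6 to 7 points on the elapsed-day reading, about 1.5 on the flow-sheet anchor, none from late scans on the visit reading. The combined +10.1 should not be quoted as the expected bias, because it stacks assumed dropout on the least favorable anchor.

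Separately, 7.2.3 starts PFS and OS at an event that does not occur in this single-arm study. That does not move the 24-week rate, which already starts at treatment, but it needs correcting.

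A reader might infer that the trial's decision is at risk. It is not: this rate is secondary and descriptive, with no test or threshold, and the two-stage ORR design does not use it. The change is worth making but is not critical.

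**What to change.** 1. In 7.2.1, replace the plain percentage with the Kaplan-Meier estimate at week 24, counted from first dose. Censor patients with no event by week 24 and no tumor assessment at or after the week-24 visit at their last tumor assessment, and report how many there are. A patient whose later scan shows no PD counts as event-free at week 24. State also how a patient with no week-24 scan and PD on a later scan is classed.
2. State the anchor for week 24 and reconcile the ±3 day window (Synopsis) with the ±7 day window (6.3.2, footnote f). For this rate, assign every in-window scan to its scheduled visit, so that PD on the in-window week-24 scan is an event.
3. In 7.2.3, censor PFS at the last adequate tumor assessment, replace randomization with first dose of study treatment for PFS and OS, and state the dating rule so that the PFS curve and the 24-week rate can be reconciled.

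**Cost.** Wording and analysis only; no extra scans or patients. The reported rate may be somewhat lower. If the PFS curve keeps actual scan dates, its value at day 168 will differ from the 24-week rate (6.9 points in the ±7 day elapsed-day case), and the report must explain why. The fix assumes that leaving assessment is unrelated to progression risk. In simulation, if leavers progress at 1.5 to 2 times the hazard, with 10% to 20% leaving per visit, +1.2 to +3.6 points remain, against +10.6 to +14.4 for the plain percentage on the elapsed-day reading.

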#### 7.2.2 Overall survival (OS) rate at 6- and 12-months

The definition of 6- and 12-months OS rate is the percentage of patients who had **NOT** has an event before or at 6 or 12 months. An event is defined as follows: Death due to any cause.

#### 7.2.3 PFS and OS

PFS is measured from the time of randomization to the time of disease progression (either CNS or extra-CNS, according to RECIST 1.1), or death due to any cause. Patients who have not had an event at the time of data analysis will be censored at the date on which they are

last known to be alive and event-free, on or before the clinical data cutoff date of the respective analysis.

OS is measured from the time of randomization to the time of death. Patients who had not recorded a death event at the time of statistical analysis will be censored at the last time point the patient was known to be alive.

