## 5.5 Duration of the treatment

- Patients may continue on study therapy until disease progression or until unacceptable toxicity occurs.
- Patients will go off study therapy if any of the following occurs:
  - The patient experiences any grade 4 toxicity after 2 dose modifications, as recommended by the protocol. If treatment is held for 2 consecutive treatment cycles due to toxicity, the patient must go off treatment.
  - The patient withdraws consent from treatment or from the study as a whole.
  - There is disease progression.
  - The treating physician feels it is necessary (e.g. due to patient non-compliance or other safety concerns)

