### 6.3 Tumor Assessment during treatment

#### 6.3.1 Tumor imaging criteria—RECIST 1.1

1. The tumor response will be determined by applying **RECIST 1.1**. Assessment schedule of week 8, 16, 24 and every 12 weeks afterwards, according to the regulation of the payment of image study by National Health Insurance. The measurability of a tumor is defined as follows:

- **Measurable disease** - the presence of at least one measurable lesion. If the measurable disease is restricted to a solitary lesion, it can be still be considered as a measurable target according to its clinical course.
- **Measurable lesions** - lesions that can be accurately measured in at least one dimension with longest diameter  $\geq 20$  mm using conventional techniques or  $\geq 10$  mm with spiral CT scan.
- **Non-measurable lesions** - all other lesions, including small lesions (longest diameter  $< 20$  mm with conventional techniques or  $< 10$  mm with spiral CT scan) and inflammatory breast disease.

All measurements should be taken and recorded in metric notation, using a ruler or calipers. All baseline evaluations should be performed as closely as possible to the beginning of treatment and never more than 4 weeks before the beginning of the treatment.

The same method of assessment and the same technique should be used to characterize each identified and reported lesion at baseline and during follow-up. Clinical lesions including skin nodules and palpable lymph nodes will be considered measurable when they are superficial. For the case of skin lesions, documentation by color photography, including a ruler to estimate the size of the lesion, is recommended.

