#### **6.3.4 Follow up of patient status**

- Patients with grade 3 or 4 toxicity after treatment will be followed-up until the toxicity resolved to grade 1 or 2.
- All patients will be followed for survival at least 6 months after end-of-treatment. Follow-up interval should be every 8 weeks +/- 1 week.

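### PFS censoring is not tied to a tumour assessment, and the 24-week PFS rate counts patients who stop early and are not scanned as successes

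*Combined protocol and SAP*

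**What the plan says.** - **Event.** Section 7.2.1 counts two events: "Disease progression (PD according to RECIST 1.1") and death from any cause. Section 7.2.3 uses the same two for PFS.
- **Censoring.** Section 7.2.3 censors patients without an event at the date they were "last known to be alive and event-free, on or before the clinical data cutoff date". No tumour assessment is mentioned. The OS rule in the same section refers only to being alive.
- **24-week rate.** Section 7.2.1: "The definition of 24-week PFS rate is the percentage of patients who had" no event by week 24. It names no estimator and has no rule for patients not scanned to week 24. Section 8.2.1 promises only descriptive statistics with confidence intervals.
- **Scans.** Section 6.3 is headed "Tumor Assessment during treatment". Section 6.3.2 sets them at baseline, then "8 weeks, and 16 weeks and 24 weeks and every 12 weeks afterwards".
- **After treatment.** Section 6.3.4: "All patients will be followed for survival at least 6 months after end-of-treatment". Table 8, footnote i: "Survival follow-up interval is 8 weeks +/- 1 weeks for at least 6 months or death". No section requires scans after a patient stops without progression.
- **Stopping without progression.** Section 5.5 provides for it: "If treatment is held for 2 consecutive treatment cycles due to toxicity, the patient must go off treatment". It also lists withdrawal of consent and the physician's decision.

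**The concern.** Apart from death, a PFS event can be recorded only if the tumour is assessed. Take a patient who stops for toxicity at week 10 and is reached by telephone at week 26. No progression is on record and the patient is alive. Section 7.2.3 can be read to censor PFS at week 26, although nothing after the last scan could have shown progression. The patient stays in the risk set over time in which only death can be recorded as an event.

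Section 7.2.1 reaches the same result by another route. It does not use the censoring rule at all, and this patient simply has no event by week 24.

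Both routes favour the treatment, and more so the more often it is stopped for reasons other than progression. PFS and its 24-week rate are named secondary endpoints of an open-label, single-arm trial with investigator-assessed response, so one data set should not support two PFS results.

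**Working it through.** **The plan's own figures.** No figure is given for PFS. The only sizing figure is for ORR. An exact Simon minimax search with P0 = 5%, P1 = 20%, one-sided alpha 0.05 and power 80% returns 13 patients in stage 1 (stop if no responses) and 27 in total. Success needs at least 4 responses; exact alpha is 0.0416 and power 0.801. Then 27/0.9 = 30. The design reproduces and does not depend on this point.

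**Inputs from the plan.** Scans at weeks 8, 16, 24, then every 12 weeks (6.3.2). Survival contact for 6 months (26 weeks) after treatment (6.3.4). Events are progression or death.

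**Assumed inputs (not in the plan).** Exponential time to progression with median m = 12, 20 or 30 weeks. Stopping without progression makes up a share f = 10%, 20% or 30% of the combined hazard. Median survival after progression is 40 weeks. There are no scans after stopping, stopping is independent of progression, and data cutoff falls 52 to 156 weeks after start. The 20-week case is close to the 4.6-month median PFS that the background quotes for pazopanib (4.6 × 52/12 = 19.9 weeks); that is not an estimate for this combination.

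**Step 1: rate if scans continued.** S(24) = 2^(-24/m), which gives 25.0%, 43.5% and 57.4%.

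**Step 2: one case by hand (m = 20, f = 20%).**
- Progression rate: ln 2/20 = 0.0347 per week. Stopping rate: 0.0347 × 0.2/0.8 = 0.0087 per week.
- The chance that progression is recorded at scan k, at week s_k, is [S(s_(k-1)) - S(s_k)] × exp(-0.0087 s_k).
- S at weeks 0, 8, 16, 24: 1, 0.758, 0.574, 0.435. Chance of not having stopped by weeks 8, 16, 24: 0.933, 0.871, 0.812.
- Sum: 0.242 × 0.933 + 0.184 × 0.871 + 0.139 × 0.812 = 0.226 + 0.160 + 0.113 = 0.499.

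So 50.1% have no recorded progression by week 24, against 43.5% truly free of it. Deaths before week 24 among those who stopped lower this to 48.9% in the simulation.

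**Step 3: simulation, 400,000 patients per scenario, PFS at 24 weeks (%).**

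| m (weeks) | f | Stopped before week 24 | Scans continued | Censored at last contact | Overstatement (points) | Censored at last scan |
|---|---|---|---|---|---|---|
| 12 | 10% | 9.7 | 25.0 | 30.1 | 5.1 | 25.0 |
| 12 | 20% | 20.3 | 25.0 | 35.8 | 10.8 | 25.0 |
| 12 | 30% | 31.8 | 25.1 | 42.1 | 17.0 | 25.1 |
| 20 | 10% | 6.9 | 43.6 | 46.1 | 2.5 | 43.5 |
| 20 | 20% | 14.7 | 43.4 | 48.9 | 5.5 | 43.3 |
| 20 | 30% | 23.6 | 43.5 | 52.4 | 8.9 | 43.4 |
| 30 | 10% | 5.0 | 57.4 | 58.7 | 1.3 | 57.4 |
| 30 | 20% | 10.9 | 57.5 | 60.4 | 2.9 | 57.4 |
| 30 | 30% | 17.9 | 57.4 | 62.3 | 4.9 | 57.3 |

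The last three result columns are based on Kaplan-Meier estimates.

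**Step 4: the raw percentage.** The section 7.2.1 percentage equals the last-contact column in all nine scenarios, because nobody is censored before week 24 under that rule. Changing the censoring date alone does not repair it. In the m = 12, f = 20% case the raw rate is 36% as written. It is 38% with last-scan censoring, a run in which deaths after the last scan are also dropped. With continued scans it is 25%.

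**Step 5: median PFS.** At f = 10% and 20% the median is the same with last-contact censoring as with continued scans (16, 24 and 36 weeks), because progression is dated on the scan grid. At f = 30% it rises from 16 to 23 weeks, from 24 to 34, and from 36 to 37 (43 if survival contact runs to the cutoff).

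**Step 6: scale in this trial.** At m = 20, 2.5 to 8.9 points of 27 patients is 0.7 to 2.4 patients. The standard error of a 43% rate is √(0.43 × 0.57/27) = 9.5 points.

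**The case against.** **The wording may already require a scan.** A telephone contact cannot show that a patient is free of RECIST progression, so the phrase in 7.2.3 can be read as the last tumour assessment. The OS sentence leaves out the event-free condition, which supports that reading. This stands: a reader might infer that 7.2.3 definitely counts unscanned time, but the text is ambiguous rather than plainly wrong. It does not rescue 7.2.1, which makes no use of the censoring date.

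**Scans may continue.** A reader might also infer that the plan confines imaging to the treatment period. The support for that is a heading and the flow-sheet columns, and section 6.3.4 sits under the same heading while covering time after treatment. The schedule runs by calendar week with no stated end, and section 10.3 says insurance reimburses imaging every 3 months. The documents neither require nor rule out scans after stopping. Any that are done would shrink the bias.

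**The size is assumed.** This stands. The 10% drop-out allowance in section 8.1 is a different quantity from the share stopping without progression. Table 8, footnote j, foresees later cycles on lenvatinib alone, which would reduce complete stopping. At the lowest share the bias is well inside sampling error, though it always runs in the same direction.

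**The endpoints are secondary and descriptive.** This is true. No threshold or test is attached to PFS.

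**Conclusion.** The point holds as two linked defects. Section 7.2.3 leaves the PFS censoring date open to a reading in which unscanned time counts as progression-free. Section 7.2.1, followed as written, counts patients who stop early, go unscanned and have no event by week 24 as successes under either reading.

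The overstatement of the 24-week rate is about 1 to 17 points over the assumed range, and about 3 to 9 points at a median near 20 weeks. It is nil if nobody stops without progression. It would be wrong to infer that median PFS is inflated in general: it is unchanged at shares of 10% and 20% and moves only near 30%. It would also be wrong to infer that last-scan censoring removes all bias. It recovers the true rate here because the simulation makes stopping independent of progression; if patients who stop have a different risk of progression, it is biased too.

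Confidence is good on the text and the direction and moderate on the size. The ORR endpoint and the 13/27/30 design are not touched.

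**What to change.** - **Section 7.2.3:** censor PFS at the date of the last evaluable tumour assessment without progression, or day 1 if there is none. Keep last-contact censoring for OS only. Say how a death after the last scan is treated. The last-scan column above drops such deaths; counting them as events changes it little in these scenarios.
- **Section 7.2.1:** estimate the 24-week rate by Kaplan-Meier from these data. As a sensitivity analysis, count patients not assessed through week 24 as non-successes, which gives a conservative figure. Both edits are needed, because the first alone leaves the raw percentage as it is.
- **State the assumption:** the estimate takes stopping without progression to be independent of progression. Report how many patients stopped this way before week 24, so that readers can judge the possible size.

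The cost is a few sentences. No new scans or visits are needed, since scan dates are already collected. Follow-up for PFS becomes slightly shorter and the result slightly less favourable. If the sponsor already means the last scan, the edit to 7.2.3 changes nothing in the analysis.
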